3.2 SECONDARY OBJECTIVES

- Efficacy Objectives:
 - a. To determine progression-free survival (PFS) on COTEZO in cohorts of advanced rare tumors per RECIST v1.1 and irRECIST.
 - b. To determine overall survival (OS) on COTEZO in cohorts of advanced rare tumors.
 - c. To determine disease control rate (DCR) and duration of response (DOR) on COTEZO in cohorts of advanced rare tumors per RECIST v1.1 and irRECIST.
 - d. To determine objective response rate (ORR) per immune-related RECIST criteria.
- Safety Objectives:
 - a. To determine safety profile and adverse events encountered by patients with advanced rare tumors treated with COTEZO.
- Translational Objectives:
 - a. To collect and bank tumor tissue and peripheral blood for future correlative analyses from patients with advanced rare tumors treated with COTEZO.

4. STUDY DESIGN

4.1 DESCRIPTION OF THE STUDY

This study will be a single-arm, open-label, non-randomized trial evaluating the combination of cobimetinib, a highly selective, oral, reversible inhibitor of MEK1 and MEK2, and atezolizumab, a fully humanized monoclonal programmed cell death ligand 1 (PD-L1) antibody, in multiple cohorts of patients with advanced rare tumors. After signing informed consent, all eligible patients will be treated with a combination of cobimetinib and atezolizumab (See Study schema). The primary objective is to assess the efficacy of this combination as measured by ORR using RECIST v1.1.

[figure not shown]
Tumor response will be evaluated according to RECIST v1.1 (see Appendix 6). Any evaluable and measurable disease must be documented at screening and re-assessed at each subsequent tumor evaluation. Investigators will assess tumor response at 8 week intervals, regardless of any dose delays or treatment cycle. Treatment beyond initial investigator-assessed RECIST 1.1-defined progression will be considered in subjects experiencing investigator-assessed clinical benefit and tolerating study therapy (especially during the flare time-window of the first 12 weeks of treatment to account for expected delayed response). In such cases confirmation of progression is recommended minimum 4 weeks after the first immune-related PD assessment. Such subjects must discontinue therapy when further progression is documented.

All patients will be closely monitored for safety and tolerability during all cycles of therapy, at the treatment discontinuation visit, and during the follow-up period. The NCI CTCAE v4.0 will be used to characterize the toxicity profile of the study treatments on all patients.

After discontinuation of study treatment, patients may receive any subsequent line therapy as directed by their treating physician.

Patients who discontinue treatment for reasons other than disease progression (e.g., toxicity) will continue scheduled tumor assessments until disease progression, withdrawal of consent, study termination by Sponsor, or death, whichever occurs first. In the absence of disease progression, tumor assessments should continue regardless of whether patients start a new anti-cancer therapy, unless consent is withdrawn. All patients will be followed for survival unless consent is withdrawn.

Figure 1: Study Schema

[figure not shown]

Abbreviation: CR, complete response; IV, intravenous; mg, milligram; PD, progressive disease; PO, orally; RECIST, Response Evaluation Criteria in Solid Tumors v1.1; SD, stable disease.

*Treatment beyond initial RECIST PD can be considered in subjects experiencing clinical benefit and tolerating study therapy. In such cases confirmation of PD is recommended minimum 4 weeks after the first immune-related PD assessment. Such subjects will discontinue therapy when further progression is documented.

All patients on the study will be enrolled and receive (Figure 1): Cobimetinib 60 mg orally on Days 1–21 plus atezolizumab 840 mg IV on Day 1 and Day 15 in a 28-day cycle.

Figure 2: Treatment Schedule

The expected total length of time on study is anticipated to be approximately 15 months, with 2 weeks spent in screening, 4 weeks in washout, 12 months receiving therapy, and 2 months of follow-up prior to the final protocol visit.

Patients will undergo mandatory tumor biopsy sample collection, unless not clinically feasible as assessed and documented by the investigator, prior to cycle 2 days 1 (during week 4) and at the time of first evidence of radiographic disease progression according to RECIST v1.1 within 40 days after radiographic progression or prior to the start of new anti-cancer treatment, whichever

is sooner. These samples will be analyzed to evaluate tumor-infiltrating immune cells [ICs]). In addition, tumor tissue biomarkers related to resistance, disease progression, and clinical benefit of cobimetinib and atezolizumab may be analyzed.

4.2 END OF STUDY AND LENGTH OF STUDY

The final analysis will occur after full enrollment, which is expected approximately 18 months after the first patient is enrolled. The end of this study is defined as the date when the last patient, last visit (LPLV) occurs or the date at which the last data point required for statistical analysis (i.e., ORR) or safety follow-up is received from the last patient, whichever occurs later. LPLV is expected to occur 30 months after the first patient is enrolled. In addition, the PI may decide to terminate the study at any time.

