Treatment beyond initial investigator-assessed RECIST 1.1-defined progression will be considered in subjects experiencing investigator-assessed clinical benefit and tolerating study therapy (especially during the flare time-window of the first 12 weeks of treatment to account for expected delayed response). In such cases confirmation of progression is recommended minimum 4 weeks after the first immune-related PD assessment. Such subjects must discontinue therapy when further progression is documented.

Figure: Study Schema

Abbreviation: CR, complete response; IV, intravenous; mg, milligram; PD, progressive disease; PO, orally; RECIST, Response Evaluation Criteria in Solid Tumors v1.1; SD, stable disease. * Treatment beyond initial RECIST PD can be considered in subjects experiencing clinical benefit and tolerating study therapy. In such cases confirmation of PD is recommended minimum 4 weeks after the first immune-related PD assessment. Such subjects will discontinue therapy when further progression is documented.

Sample size and anticipated duration	Targeted enrollment	Accrual Duration (months)	Follow-up Duration (months)
Appendiceal adenocarcinoma	20	18	12
Cutaneous squamous cell carcinoma	20	18	12
Small bowel adenocarcinoma	20	18	12
Total	60		

Eligibility Criteria:

INCLUSIONS:

For individual baskets:

- **Appendiceal Adenocarcinoma**
 - Not considered candidate for curative surgery.
- **Cutaneous squamous cell carcinoma**
 - Patients with either metastatic or locally advanced cutaneous squamous cell carcinoma that are technically resectable but in whom surgery is expected to lead to substantial function impairment or disfigurement are eligible.
- **Small bowel adenocarcinoma**

- Must be refractory or intolerant to at least one line of 5FU-based chemotherapy for metastatic disease.

General Inclusion Criteria:

1. Must have histologically or cytologically documented rare tumor as defined per protocol that is metastatic or locally advanced and unresectable.
2. Must be refractory or intolerant to standard lines of therapy.
3. Presence of radiographically evaluable disease.
4. Must have completed prior chemotherapy, immunotherapy, or radiation therapy at least 14 days prior to start of treatment and all toxicity must be resolved to CTCAE v4.0 Grade 1 (with the exception of CTCAE v4.0 Grade 2 neuropathy) prior to start of treatment.
5. ECOG Performance Status of 0-2.
6. Age \geq 18 years.
7. Tissue Parameters:

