5.6.5 Tumor and Response Evaluations

Patients will undergo tumor assessments at baseline and every 8 weeks in all cohorts assessed, regardless of dose delays, until radiographic disease progression per RECIST v1.1 or (for atezolizumab treated patients who continue treatment after radiographic disease progression) loss of clinical benefit as determined by the investigator. Thus, tumor assessments are to continue according to schedule in patients who discontinue treatment for reasons other than disease progression or loss of clinical benefit, even if they start new anti-cancer therapy. At the investigator's discretion, tumor assessments may be repeated at any time if progressive disease is suspected.

All measurable and evaluable lesions should be assessed and documented at screening. Tumor assessments performed as standard of care prior to obtaining informed consent and within 28 days prior to initiation of study treatment do not have to be repeated at screening.

Cross sectional imaging will be performed with either contrast enhanced CT or MRI. RECIST 1.1 criteria will be used to determine disease response.

If a CT scan for tumor assessment is performed in a positron emission tomography (PET)/CT scanner, the CT acquisition must be consistent with the standards for a full contrast diagnostic CT scan.

All measurable and evaluable lesions should be re assessed at each subsequent tumor evaluation. The same radiographic procedures used to assess disease sites at screening should be used for subsequent tumor assessments (e.g., the same contrast protocol for CT scans).

Response will be assessed by a blinded radiologist at the MD Anderson Quantitative Imaging Analysis Core using RECIST v1.1 (see Appendix 2) and immune-modified RECIST (see Appendix 5). Assessments should be performed by the same evaluator, if possible, to ensure internal consistency across visits. Results must be reviewed by the investigator before dosing at the next cycle.

For cutaneous squamous cell carcinoma, since “surgery (preferable) or definitive radiation therapy (with or without radiosensitizing agent)” is allowed for patients after initial response, such a definitive local therapy can only be performed after at least 1 tumor assessment.

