5.10.3 Determination of Sample Size

The primary endpoint is best ORR (PR or CR), measured as per RECIST 1.1. Three parallel single-stage phase II trials will be conducted. A total of 60 patients will be enrolled, i.e., 20 patients in each tumor group. Considering the rareness of the disease, the patient accrual rate is approximately 1 to 2 patients per month per tumor group.

Sample size calculation

For each tumor group, we will estimate the best ORR and its exact confidence interval (CI). When the sample size is 20, and the response rate is 0.3, the two-sided 95% exact CI using the Clopper and Pearson method will be (0.119, 0.543).

For each tumor group, we will also compare its overall best response rate to the historical control based on the current literature. Let p represent the overall best response rate, we will perform independent Binomial test against $H_0: p=0.1$ for each group, with a 1-sided type I error rate of 0.05. The sample size of 20 will provide 76% power to detect an improved best ORR being 30% compared to 10%.

Analysis Plan

The primary outcome is the best ORR since the start of treatment. For each tumor group, we will estimate the best response rate and its 95% exact confidence interval using the Clopper and Pearson method. And we will assess the efficacy of the combination treatment by performing the independent binomial test comparing the best response rate versus the historical control for each tumor group. The primary efficacy analyses will include all treated patients who have received at least one dose of study treatment and have baseline tumor assessment. Patients who do not receive at least 1 dose of therapy will be replaced.

For each tumor group, median DOR and corresponding 2-sided 95% CI will be reported. The association between the best ORR and other variables will be assessed using the Fisher's exact test. Time-to-event outcomes, including progression free survival (PFS) and overall survival (OS), will be estimated using Kaplan-Meier method. The log-rank test will be performed to test the difference in time-to-event distributions between patient groups. Cox proportional hazards model may be utilized to include multiple covariates in the time-to-event analysis.

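### Does Section 4.2 allow the final analysis before the last patients have been scanned, so that a data cut-off must be added?

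*Combined protocol and SAP*

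**What the plan says.** Section 4.2 contains three statements about timing.

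- On the final analysis: "The final analysis will occur after full enrollment, which is expected approximately 18 months after the first patient is enrolled".
- On the end of the study: it is the later of the last patient's last visit and "the date at which the last data point required for statistical analysis (i.e., ORR) or safety follow-up is received from the last patient".
- On that last visit: "LPLV is expected to occur 30 months after the first patient is enrolled".

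The synopsis table lists, for each cohort, 20 patients, 18 months of accrual and 12 months of follow-up. Section 4.1 describes one patient's expected time on study as including "12 months receiving therapy, and 2 months of follow-up prior to the final protocol visit".

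On assessments, Section 5.6.5 says: "Patients will undergo tumor assessments at baseline and every 8 weeks in all cohorts assessed". Section 5.10.3 says that "the patient accrual rate is approximately 1 to 2 patients per month per tumor group". It takes best response since the start of treatment as the primary outcome and analyses everyone who had at least one dose and a baseline tumor assessment. Section 5.10.1 likewise analyses ORR on all treated patients.

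**The concern.** Read alone, the first sentence makes full enrollment the only condition for the final analysis. The end-of-study sentence mentions response data from the last patient, but formally it defines when the study ends, not when the analysis is run. Nothing in Section 5.10 states a cut-off, a minimum number of scans or a minimum follow-up.

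A patient enrolled in the 8 weeks before a cut at full enrollment would have no scheduled post-baseline scan. The protocol itself expects late responses and singles out a period, "especially during the flare time-window of the first 12 weeks of treatment to account for expected delayed response", so even one scan may come early. If the cut were made at full enrollment, the last cohort to fill would have less than its stated power, and PFS, OS and DOR would be immature. In an open-label study, an unstated cut-off could also be picked after responses are known.

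The follow-up figures also seem to disagree: 12 months in the synopsis, 2 months in Section 4.1.

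**Working it through.** **1. The plan's own figure.** Inputs from Section 5.10.3: n = 20, p0 = 0.10, p1 = 0.30, one-sided alpha 0.05, exact binomial test. Requiring 4 responders gives alpha 0.133. Requiring 5 gives alpha P(X ≥ 5 | 20, 0.10) = 0.043 and power P(X ≥ 5 | 20, 0.30) = 0.762. The stated 76% is reproduced.

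**2. Patients unscanned if the cut were at full enrollment.** Eight weeks is 56 / 30.44 = 1.84 months. The expected number per cohort without a scheduled scan is accrual rate × 1.84, for a cohort still enrolling up to the cut:

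- 1 per month: 1.8
- 20/18 = 1.11 per month: 2.0
- 2 per month: 3.7

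A cohort that filled at least 8 weeks before the cut has none.

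**3. Effect on the test.** Let m treated patients have no scan and stay in the denominator as non-responders. Five responders must then come from the other 20 − m.

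| m | Power at 30% | Alpha at 10% | Expected ORR, 0.3 × (20 − m)/20 |
|---|---|---|---|
| 0 | 76.2% | 0.043 | 30% |
| 1 | 71.8% | 0.035 | 28.5% |
| 2 | 66.7% | 0.028 | 27% |
| 3 | 61.1% | 0.022 | 25.5% |
| 4 | 55.0% | 0.017 | 24% |

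Leaving them out gives the same power, because the cutoff is 5 for every n from 16 to 20. Section 5.10.3 does not allow that exclusion, however: inclusion needs only a dose and a baseline assessment.

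**4. What the planned timeline gives.** Taking the last patient as enrolled at month 18, one scheduled scan is reached at 18 + 1.84 = month 19.8, and two at 18 + 3.68 = month 21.7. By month 30 that patient has 12 months of potential follow-up, and 12 / 1.84 = 6.5, so six scheduled scans. Even at 1 patient per month, with the cohort full at month 20, one scan is reached at month 21.8. All these dates fall before the expected last visit.

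**5. Choosing the date after seeing responses.** The outcome is best response since treatment start. If a recorded response is not later withdrawn, each cohort's responder count can only stay level or rise. With 20 patients in the denominator, the count at any cut is at most the eventual count. So if the eventual response rate is 10%, the chance that any cut after full enrollment shows 5 or more responders is no greater than 0.043.

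**6. The follow-up figures.** The synopsis gives 12 months of follow-up after accrual for each cohort: 18 + 12 = month 30, which agrees with Section 4.2. Section 4.1's 2 months is one patient's follow-up after therapy. Adding its figures to the last enrollment gives 18 + 12 + 2 = month 32, two months later than Section 4.2. Both totals rest on expected or approximate durations, and therapy has no fixed length.

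**The case for a change.** The best case for a change is that an inferred intention is not a prespecified rule. Two statisticians could read Section 4.2 and cut the data at month 18 or month 30. Emerging responses will be visible: Section 5.10.3 has safety and efficacy data reviewed with the principal investigator after every 5 patients per group, and Section 5.10.4 allows up to two efficacy interims interpreted by the study team. The blinded radiology reading in Section 5.6.5 protects the measurements but not the timing. If cohorts enrolled at 2 per month right up to the cut, power would fall to between 55% and 61%. A cut-off sentence would be cheap.

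Part of this stands. The plan does not state a cut-off, and the conditional arithmetic is correct. What does not follow is that the plan leads to a poor analysis. Nothing in it calls for a cut on the day enrollment closes, and the same section treats response data from the last patient as required. Discretion over timing cannot raise the false-positive rate of the primary test under the condition in step 5. PFS and OS are Kaplan-Meier estimates with no fixed target to pass, so an early cut would make them less mature without making them invalid. Any particular scan minimum would be a reviewer's preference: one scan already removes the unscanned-patient problem, and nothing in the protocol dictates two.

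**Conclusion.** No change to the plan follows. Section 4.2 does not name a data cut-off, but its wording sets only an earliest time. The required response data from the last patient, the last visit at month 30 and the 12-month follow-up in the synopsis all point to an analysis on complete data. An analyst following the plan would wait for the last patient's scans and, with all 20 assessed, keep the stated 76% power.

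The possible loss, to about 67% with 2 unscanned patients or 55% to 61% with 3 to 4, is hypothetical. It assumes a cut at full enrollment, even accrual up to that date and a true response rate of 30%. Its direction is conservative: alpha falls below 0.043 and the observed rate is understated. The 12-month and 2-month follow-up figures measure different things, and the two-month difference between month 30 and month 32 is within the looseness of forecasts.

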4.3 RATIONALE FOR STUDY DESIGN

Study Hypothesis: Combination therapy with COTEZO will be well tolerated in patients with rare tumors and will have significant anti-tumor activity resulting in improved outcomes.

4.3.1 Rationale for Dose and Schedule for Cobimetinib and Atezolizumab

Concomitant administration of atezolizumab and cobimetinib was studied in the Phase Ib Study GP28363. Cobimetinib 60 mg on a 21/7 schedule is the approved dose and schedule of cobimetinib. For administration with cobimetinib, on a 28-day cycle, a dose of 840 mg atezolizumab administered every 2 weeks has the equivalent dose exposure as the 1200 mg every 3 weeks (21-day cycle), the standard dose for the atezolizumab monotherapy. In Study GP28363 atezolizumab was dosed concurrently with cobimetinib at 800 mg IV q2w. The 840 mg dose is expected to be similar to the 800 mg dose of atezolizumab dose and selected in this study to simplify dose administration.

4.3.2 Rationale for the Use of Immune-Modified RECIST

Increasing clinical experience indicates that traditional response criteria (e.g., RECIST v1.1 and World Health Organization criteria) may not adequately assess the activity of immunotherapeutic agents because initial radiographic evidence of disease progression does not necessarily reflect therapeutic failure. Patients can experience a response in the presence of new lesions or after an increase in tumor burden. Thus, this study will employ immune-modified RECIST for tumor assessments to account for the possible appearance of new lesions and allow radiographic progression to be confirmed at a subsequent assessment (see Appendix 5). It is required that radiographic progression is confirmed at a subsequent tumor assessment to take into account the potential for pseudoprogression (caused by immune cell infiltration). Given the proposed immunomodulatory mechanism of action of atezolizumab and the possibility of observing delayed responses, use of immune-modified RECIST will allow for the capture of a greater proportion of potential responses and allow patients to derive maximum clinical benefit.

4.3.3 Rationale for Biomarker Assessments

Published results suggest that the expression of PD-L1 in tumors correlates with response to anti-PD-1 and anti-PD-L1 therapy (**Topalian et al. 2012; Herbst et al. 2014; Borghaei et al. 2015; Fehrenbacher et al. 2016; Herbst et al. 2016; Rosenberg et al. 2016**). In the current study, archival or baseline tumor specimens will be collected from patients and tested for PD-L1 expression by a central laboratory during the screening period. In addition to the assessment of PD-L1 status, other exploratory biomarkers, such as potential predictive and prognostic biomarkers related to the clinical benefit of atezolizumab, tumor immunobiology, mechanisms of resistance, or tumor type, may be analyzed.

Patients will undergo mandatory tumor biopsy sample collection, if deemed clinically feasible by the investigator, after 3 weeks of therapy and at the time of first evidence of radiographic disease progression to evaluate the utility of the biopsy in distinguishing pseudoprogression (caused by immune cell infiltration) from true progression. In addition, tumor tissue biomarkers related to resistance, disease progression, and clinical benefit of atezolizumab may be analyzed.

Blood samples will be collected at baseline and during the study to evaluate changes in surrogate biomarkers. Changes in biomarkers such as cytokines associated with T cell activation, circulating tumor DNA (ctDNA) concentration, and lymphocyte subpopulations may provide evidence of biologic activity of atezolizumab in humans. Correlations between these biomarkers and safety and efficacy endpoints will be explored to identify blood-based biomarkers that might predict which patients are more likely to benefit from atezolizumab.

Tumor tissue and blood samples collected at baseline and, if deemed clinically feasible, tumor tissue collected at 8 weeks of therapy and at the time of progression will enable NGS and RNA profiling to identify germline and/or somatic mutations that are predictive of response to study drug, are associated with progression to a more severe disease state, are associated with acquired resistance to study drug, are associated with susceptibility to developing adverse events, or can increase the knowledge and understanding of disease biology.

Genomics is increasingly informing researcher's understanding of disease pathobiology. WGS provides a comprehensive characterization of the genome and, along with clinical data collected in this study, may increase the opportunity for developing new therapeutic approaches.

